Mothers were recruited in maternity wards of the 12 participating hospitals shortly after giving birth and, after consenting, were administered a 30-minute baseline interview. They then were asked to consent to the cash gifts. The "high-cash gift" treatment group mothers (40% of all mothers) are receiving unconditioned cash payments of \$333 per month (\$4,000 per year) via debit card for 52 months. Mothers in the "low-cash gift" comparator group (60% of all mothers) are receiving a nominal payment – \$20 per month, delivered in the same way and also for 52 months. The 40/60 randomization assignment is stratified by site, but not by hospitals, within each of the four sites.

BFY was originally formulated to study the effects of monthly unconditional cash transfers on child development for the first three years of life, with the cash gifts set to be distributed for 40 months (3 years, 4 months). In response to the COVID-19 pandemic and the need to postpone in-person research activities, the cash transfers were extended for an additional year, through 52 months (4 years, 4 months), enabling us to postpone in-person direct child assessments to age 4. Interviews conducted at child ages 1, 2 and 3 are providing information about family functioning as well as several maternal reports of developmentally-appropriate measures of children's cognitive and behavioral development. The current analysis plan includes lab-based assessments at child age 4.

Conditional on participants' consent and our success in securing agreements with state and county agencies, we are also collecting state and local administrative data regarding parental employment, utilization of public benefits such as Medicaid and Supplemental Nutrition Assistance Programs (SNAP), and any involvement in child protective services. (We have worked with state and local officials to ensure to the extent feasible that our cash gifts are not considered countable income for the purposes of determining benefit levels from social assistance programs.)

The compensation difference between families in the high and low cash gift groups will boost family incomes by \$3,760 per year, an amount shown in the economics and developmental psychology literatures to be associated with socially significant and policy relevant improvements in children's school achievement. After accounting for likely attrition, our total

Analysis Plan for Phase 1

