Our basic empirical approach will use the survey and neuroscience data to compare the pooled cross-city \$333/month and \$20/month groups on a wide range of family process and child outcome measures. Because of random assignment, the low cash gift group average outcomes enable us to identify the average outcomes corresponding to the counterfactual state that would have occurred for individuals in the high cash gift group if they had not been offered the additional \$313/month income supplement. Therefore, differences in outcomes for the high compared with the low group (after random assignment) can be interpreted as estimates of causal treatment effects of the \$313/month higher income (regardless of whether treatment-group participants actually expend all of the funds.) These are commonly known as intent-to-treat effects.

Estimation strategy. We illustrate our approach to estimation in a simple regression framework. The “Intent-To-Treat effect” (ITT) is captured by the estimate of the coefficient π_1 in a regression of some child or family process outcome (Y) on a dichotomous indicator for assignment (Z) to the high payment group as in (1).

$$(1) Y = Z\pi_1 + X\beta_1 + \varepsilon_1$$

We have experienced extremely low rates of “non-compliance” with the offer of cash gifts paid via the debit cards, with less than 10 of the 1,000 participants never having charged anything on their debit cards. We will adjust standard errors using robust variance estimation techniques (Cameron et al. 2008). We will estimate (1) without and then with baseline demographic child and family characteristics (X) to improve the precision of our estimates by accounting for residual variation.

Baseline measures, all gathered prior to random assignment, have been checked for adequate variation and sufficient independence from other baseline measures. They include: dummy variables for three of the four sites; mother’s age, completed schooling, household income, net worth, general health, mental health, race and Hispanic ethnicity, marital status, number of adults in the mother’s household, number of other children born to the mother, whether the mother smoked or drank alcohol during pregnancy and whether the father is currently living with the mother; and child’s sex, birth weight, gestational age at birth, and birth order.

Analysis Plan for Phase 1

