Statistical power. The compensation difference between families in the high- and low-cash gift groups amounts to \$313 per month and \$16,276 over the course of the 52 months. This amount is in the range of income increases associated with child impacts of around .20 sd in studies of welfare experiments and the EITC ([name], Morris & Rodrigues, 2011; Morris, [name], Clark-Kauffman, 2005; Dahl & Lochner, 2012). After accounting for likely 20% attrition in the age-4 lab visit, and in the absence of adjustments for sample clustering within hospitals or increased precision owing to the inclusion of baseline covariates in our impact estimates, the sample size of 800 at age 4, divided 40%/60% between high and low payment groups, provides 80% statistical power to detect a .219 sd impact at $p < .05$ in a two-tailed test on cognitive functioning and family processes. The use of baseline covariates in estimation models will improve this power, while the use of bootstrap standard errors will decrease it. Based on exploratory analyses of age-3 cognitive outcomes in the Fragile Families study, we expect that these two offsetting factors will have little net impact on the size of our estimated standard errors.

Multiple comparisons. One strength of our study is the collection of survey, neuroscience lab and administrative data on a wide range of outcomes and explanatory pathways. However, the probability of rejecting a true null hypothesis for at least one outcome is greater than the significance level used for each test. We will address the possibility of false positives while minimizing the reduction in statistical power to detect meaningful effects. Best-practice methods differ across disciplines so we will draw from multiple approaches with the goal of ensuring that results from one approach are consistent with results from others (Romano & Wolfe, 2005; Porter, 2018; Benjamini, 2010; Holm, 1979, Westfall & Young, 1993; Schochet, 2008). Where possible we have aggregated measures used to test our pre-registered hypotheses into indexes. In the case of related measures that cannot be aggregated into a single index, we will estimate the statistical significance of the entire family (“familywise error rate”) using stepdown resampling methods in Westfall and Young (1993; Westfall, Tobias, Wolfinger, 2011). Pre-registered clusters of measures are identified with grey bars in appendix tables.

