These two measures were not initially preregistered for analyses of child outcomes (Receptive One-Word Picture Vocabulary Test, Minnesota Executive Function Scale, Child Behavior Checklist, Resting Brain Activity, Matrices, Reading House, and Developmental Condition Diagnosis, age/sex adjusted BMI percentile and maternal report of child health) and maternal outcomes (depression, anxiety, and Body Mass Index (BMI)). Child age controls for age-related developmental differences that may affect both preregistered child and maternal outcomes, while the indicator for the interviewer/assessor has been added to account for any idiosyncratic assessor component to variation in preregistered child and maternal measures based on lab or survey assessments.

Analysis Plan for Phase 1

References

- Benjamini, Y. (2010). Simultaneous and selective inference: Current successes and future challenges. *Biometrical Journal*, 52(6), 708–721. <https://doi.org/10.1002/bimj.200900299>
- Cameron, A. C., Gelbach, J. B., & Miller, D. L. (2008). Bootstrap-based improvements for inference with clustered errors. *The Review of Economics and Statistics*, 90(3), 414–427. <https://doi.org/10.1162/rest.90.3.414>
- Dahl, G. B., & Lochner, L. (2012). The Impact of Family Income on Child Achievement: Evidence from the Earned Income Tax Credit. *American Economic Review*, 102(5), 1927–1956. <https://doi.org/10.1257/aer.102.5.1927>
- [name], G. J., Morris, P. A., & Rodrigues, C. (2011). Does money really matter? Estimating impacts of family income on young children's achievement with data from random assignment experiments. *Developmental Psychology*, 47(5), 1263–1279. <http://dx.doi.org/10.1037/a0023875>
- Holm, S. (1979). A Simple Sequentially Rejective Multiple Test Procedure. *Scandinavian Journal of Statistics*, 6(2), 65–70. <https://www.jstor.org/stable/4615733>
- Manski, C. F. (1989). Anatomy of the Selection Problem. *The Journal of Human Resources*, 24(3), 343–360. <https://doi.org/10.2307/145818>
- Manski, C. F. (1990). Nonparametric Bounds on Treatment Effects. *The American Economic Review*, 80(2), 319–323. <https://www.jstor.org/stable/2006592>

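### The SAP cites a clustered-error bootstrap without naming its cluster level or variant; individual randomisation within site does not need clustering on 12 hospitals, and applying it would cost power or error control

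*SAP*

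**What the plan says.** Under Estimation strategy, the Phase 1 and Phase 2 plans contain the same sentence: "We will adjust standard errors using robust variance estimation techniques (Cameron et al. 2008". The reference lists give the title of that paper as "Bootstrap-based improvements for inference with clustered errors". Neither section names a cluster variable, a bootstrap variant or a reference distribution.

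Hospital appears as a cluster level only under Statistical power, in both phases, as something the calculation leaves out: "in the absence of adjustments for sample clustering within hospitals or increased precision owing to the inclusion of baseline covariates". Phase 1 then says that covariates will raise power, "while the use of bootstrap standard errors will decrease it", and continues: "we expect that these two offsetting factors will have little net impact on the size of our estimated standard errors". Phase 2 repeats the hospital caveat but has neither the bootstrap sentence nor the offset sentence.

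On design, the Phase 1 Project Summary describes random assignment of individuals within each metropolitan area, recruitment through 12 hospitals, and this rule: "The 40/60 randomization assignment is stratified by site, but not by hospitals, within each of the four sites".

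In both phases the site dummies are listed among the baseline covariates X. The model to be fitted first, without X, therefore omits site.

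**The concern.** The stated contrast is the effect of individual assignment within site. Given site, one mother's assignment is independent of another's, and a hospital will in general hold both arms. Outcomes that are correlated within hospitals do not by themselves invalidate individual-level robust standard errors for that contrast.

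Resampling hospitals treats 12 clusters as the sampled units and leaves at most 11 degrees of freedom. Depending on the variant, the analysis then either keeps its error rate and gives up power, or keeps its apparent power and rejects too often. Because the variant is not named, it could also be chosen after the data are seen. The choice affects the confidence interval and p-value of every outcome analysed with the SAP's regression equation (1).

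**Working it through.** **Inputs from the documents.** N = 800 split 40/60, so 320 and 480 (Statistical power, both phases). Site sizes 121, 295, 295 and 289 (Project Summary), multiplied by 0.8 for the expected 20% attrition. 12 hospitals. Two-sided α = .05.

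**Assumptions, not in the documents.** Three hospitals per site, either equal in size or split 70/20/10; hospital ICC 0, .05 or .10; the same treatment effect in every hospital.

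**Step 1: the plan's own power figure.** The standard error in SD units is √(1/320 + 1/480) = .0722. The detectable effect at 80% power, two-sided, is (1.960 + 0.842) × .0722 = .202 SD. This agrees with Phase 2's .20. One-sided, (1.645 + 0.842) × .0722 = .179, which agrees with Phase 2's .18. Phase 1's .219 for the same N, split, α and power does not reproduce: power at .219 is 85.9%. That is a separate matter to reconcile. The checks below use .202.

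**Step 2: the cost of 11 degrees of freedom alone.** Keep the standard error at .0722 and replace the normal reference by t with 12 − 1 = 11 degrees of freedom (critical value 2.201). The noncentrality is .2022/.0722 = 2.80. Power falls from 80% to 72.3%.

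**Step 3: simulation.** There were 20,000 trials per setting, with individual 40/60 randomisation within site and least squares on treatment plus site dummies. Four methods were compared: individual-level robust errors (HC1); a restricted wild cluster bootstrap-t over all Rademacher sign patterns; hospital-clustered errors with normal cut-offs; and hospital-clustered errors with t(11) cut-offs. Simulation error is about √(.05 × .95/20,000) = 0.15 points for size and √(.8 × .2/20,000) = 0.28 points for power. Entries are two-sided type I error / power at .2022 SD, in percent.

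| Hospitals | ICC | Individual robust | Wild cluster bootstrap | Clustered, normal (size only) | Clustered, t(11) |
|---|---|---|---|---|---|
| Equal | 0 | 4.9 / 80.0 | 5.0 / 71.1 | 7.7 | 5.2 / 72.7 |
| Equal | .05 | 4.9 / 80.2 | 5.2 / 71.4 | 8.1 | 5.4 / 73.2 |
| Equal | .10 | 4.8 / 81.3 | 4.6 / 73.4 | 8.1 | 5.0 / 75.0 |
| 70/20/10 | 0 | 5.1 / 80.0 | 5.0 / 63.2 | 10.0 | 7.2 / 74.8 |
| 70/20/10 | .05 | 5.0 / 80.7 | 5.2 / 63.9 | 10.0 | 7.0 / 75.6 |
| 70/20/10 | .10 | 5.1 / 81.7 | 4.9 / 65.2 | 9.7 | 7.0 / 76.8 |

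Compared row by row, the wild cluster bootstrap costs 8 to 9 points of power with equal hospitals and about 17 points with the 70/20/10 split. Individual-level robust errors keep their size at every ICC tried.

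**The case against.** **The plan does not say it will cluster on hospital.** This stands. The estimation sections speak only of robust variance estimation, and the power text mentions hospitals as an adjustment not made. The inference is reasonable for Phase 1, where the cited title, the hospital caveat and the bootstrap sentence point the same way; an individual-level bootstrap at n = 800 would hardly change power. It is weaker for Phase 2, which has only the citation and the caveat.

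**The power cost is disclosed and said to be offset by covariates.** It is disclosed, for Phase 1. But no R² or other figure is given, and the stated basis is age-3 cognitive outcomes in another cohort. The covariate gain is equally available without clustering, so the offset gives no reason to cluster. The simulations used site dummies only, so they do not measure that gain.

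**Clustering could serve a wider target.** The protocol's Enrollment Procedures seek external validity for poor families with newborns in general. The simulations held the effect constant across hospitals. Suppose it varied with SD .10 to .15 over 12 equal hospitals (an assumption). The variance for that wider target would be .00521 + .10²/12 = .00604, up to .00521 + .15²/12 = .00708, and a nominal 5% test with individual-level errors would reject about 7% to 9% of the time. This stands as a limit on what individual-level inference covers. The SAP, however, defines its contrast as intent-to-treat in the randomised groups and states no aim of inference to a population of hospitals.

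**Conclusion.** The point holds as a gap in specification with a conditional cost. The SAP cites a clustered-error method that the randomisation does not require, and it leaves the cluster level, variant and reference distribution open. If errors are clustered on the 12 hospitals, the trial either loses about 8 to 17 points of power at .202 SD (wild cluster bootstrap) or runs at about 8-10% two-sided type I error (normal cut-offs). For the stated contrast there was no gain in validity in any setting tried. These sizes rest on the assumed hospital counts, splits and ICC.

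A reader might infer more than the documents support:

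- **That hospital clustering is the committed plan.** No sentence says so.
- **That power is lost and false positives rise together.** They are alternatives: the wild bootstrap held 4.6-5.2%, and no text proposes normal cut-offs.
- **That the damage is much larger because one hospital dominates each site.** The documents give no hospital sizes, and the 70/20/10 split already has a dominant hospital.
- **That every registered outcome is affected.** The age-4 mixed-ANOVA and the ages 6 and 8 mixed-effects band analyses of EEG use a different model.
- **That Phase 1's .219 already contains a clustering penalty.** A t(11) reference gives 78.9% power there, which is close, but the text says no clustering adjustment was made.

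**What to change.** - **Estimation strategy, both phases.** For the regression-based outcomes, name heteroskedasticity-robust (HC2 or HC3) standard errors at the mother/child level as primary, and drop or replace the clustered-bootstrap citation.
- **Site.** Keep the site dummies in every model, including the one without other covariates, because site is the randomisation stratum.
- **Hospital clustering.** Report it at most as a sensitivity analysis, with a named small-cluster method and reference distribution.
- **Statistical power, Phase 1.** Revise the bootstrap and offset sentences to match the named method. The caveats in both phases about what the calculation excludes are true and may stay.
- **Timing.** Declare the Phase 1 change as made after age-4 data collection, since the Phase 2 Attrition section already reports age-4 response counts.

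The cost is a few sentences and one option in the code. The downside is that inference is then for the enrolled sample and not for a wider population of hospitals, and the SAP should say so.

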NCT03593356 July 3, 2025

**Household Income and Child Development in the First Years of Life (Baby's First Years)
Statistical Analysis Plans for Phase 1 and Phase 2**

Our Analysis Plan for Phase 1 (dated December 13, 2022) covers hypotheses for data proposed to be collected in our age 4 follow-up. (Analytic plans for hypotheses for data collected in our ages 1, 2 and 3 follow-ups are available through the “Record History” link on the study’s clinicaltrials.gov page.)

Our Phase 2 Analysis Plan (dated June 29, 2024) covers hypotheses for data proposed to be collected in our ages 6 and 8 follow-ups.

This document begins with the December 13, 2022 Phase 1 Plan, followed by the June 29, 2024 Phase 2 Plan. An appendix to this document includes summary charts of all hypotheses and their associated measures for data collected at ages 1, 2, 3, 4, 6, and 8. Child-related hypotheses and measures are listed in Table 9; maternal- and family-related hypotheses and measures are listed in Table 10.

As described in addenda to the Phase 1 and Phase 2 plans, we made two changes to our list of control variables on July 3, 2025. Specifically, in the revised plan’s analyses of age 4, 6 and 8 preregistered child and maternal outcomes, we added to our list of controls i) the child’s age at the time of the assessment and ii) a dummy-variable indicator for the interviewer or of the staff member administering the assessments.

Analysis Plan for Phase 1

Baby's First Years Phase 1: Summary, Pre-registered Hypotheses, Analysis Strategies

December 13, 2022

Project Summary

In the Baby's First Years (BFY) study, one thousand infants born to mothers with incomes falling below the federal poverty threshold in four metropolitan areas in the United States were assigned at random within each of the metropolitan areas to one of two cash gift conditions. The sites are: New York City, the greater New Orleans metropolitan area, the greater Omaha metropolitan area, and the Twin Cities. IRB and recruiting issues led to a distribution of the 1,000 mothers across sites of 121 in one site (the Twin Cities), 295 in two of the other sites (New Orleans and Omaha) and 289 in New York. (We have also randomly sampled 80 of the participating families in the Twin Cities and New Orleans to participate in an in-depth qualitative study, but do not elaborate on those plans in this document.)

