Data release. We are releasing data and documentation from our study to the research community approximately 18 months following the end of each data collection wave to enable independent researchers to pursue replication, mediation, moderation as well as other related analytic questions.

Age-4 Resting EEG Hypotheses and Analysis Plan.

Following our publication of Age-1 resting EEG treatment impacts (Troller-Renfree et al., 2022), we amended our Age-4 resting EEG analysis plan to include primary and secondary hypotheses. The original preregistration of Age-1 EEG data included hypotheses across multiple frequency bands. However, due to participant refusal of EEG, the rejection of artifact-laden EEG files, and the high correlation between EEG bands as well as the expected effect size and consistency of the hypothesized effects, we were left with inadequate statistical power for

Analysis Plan for Phase 1

multiple hypothesis testing across bands. As we have uniform, directional hypotheses for all three mid- to high-frequency bands, we have updated this analysis plan to instead include an index of mid- to high-frequency power (described below; primary hypothesis) as well as more traditional neuroscientific investigation of power within bands (described below; secondary hypothesis). Please see the history of preregistrations, including analysis plans, to see a history of how Age-1 EEG findings altered our preregistered analyses.

For our primary hypothesis, we will test whether the high-cash gift group has more mid- to high-frequency power than the low cash gift group, we will create a single composite measure that aggregates across the portion of the spectrum defined by the three mid-to-high-frequency bands (alpha, beta, and gamma power), from 7-45 Hz. Because this approach is focused on estimating intent-to-treat differences in a single index score, there is no need for multiple-testing adjustments. Covariates will include all preregistered covariates as well as the number of artifact-free epochs contributed by each participant. Models will be examined with and without preregistered baseline covariates as above, and we will conduct sensitivity checks to evaluate whether missing data might be biasing estimates, as described above.

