"Take-up" of the cash gifts is virtually universal, with fewer than six families never having used their debit cards by child age 3. We will adjust standard errors using robust variance estimation techniques (Cameron et al. 2008). We will estimate (1) without and then with baseline demographic child and family characteristics (X) to improve the precision of our estimates by accounting for residual variation. These baseline measures, all gathered prior to random assignment, have been checked for adequate variation and sufficient independence from other baseline measures. They include: dummy variables for three of the four sites; mother's age, completed schooling, household income, net worth, general health, mental health, race and Hispanic ethnicity, marital status, number of adults in the mother's household, number of other children born to the mother, whether the mother smoked or drank alcohol during pregnancy and whether the father is currently living with the mother; and child's sex, birth weight, gestational age at birth, birth order and interview/assessor ID. For child outcomes we also control for child's age in months at the time of the survey/assessment.

Analysis Plan for Phase 2

We will apply our regression estimation strategy to the assessment-based measures of cognitive, language, self-regulation, and socio-emotional functioning and EEG measures of brain activity gathered at ages 6 and 8. To investigate family process impacts, we will apply our estimation strategy to maternal and family measures gathered at child ages 6 and 8.

Attrition. The greatest threat to internal validity is bias from sample attrition overall, within site, and differential attrition rates by treatment status overall and within site. We will carefully track response rates by site, by treatment status across sites, and then treatment status within site. Response rates were very high for the ages 1-3 data collections and varied across measures at age 4. Of the original 1,000 recruited participants, we secured interviews with 931 at age 1, 922 at age 2, and 922 again at age 3. By age 4, 5 mothers and 5 children had died and we gathered information on between $n=634$ (for child EEG) to $n=882$ (for maternal reports of behavior problems) of the remaining 990 families.

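### The fit of equation (1) without covariates omits the site strata, so its standard errors are slightly too wide, and the plan does not say which of its two fits tests the registered hypotheses

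*SAP*

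**What the plan says.** On design, the SAP (Phase 1, Project Summary) states: "The 40/60 randomization assignment is stratified by site, but not by hospitals, within each of the four sites". The Phase 2 summary repeats this. The site sizes are "121 in one site (the Twin Cities), 295 in two of the other sites (New Orleans and Omaha) and 289 in New York".

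On analysis, equation (1) in both phases contains only the treatment indicator Z and the vector X. Under Estimation strategy the plan says "We will estimate (1) without and then with baseline demographic child and family characteristics (X) to improve the precision of our estimates". Its list of the baseline measures opens with the strata: "They include: dummy variables for three of the four sites". Phase 2 uses the same wording and the same opening to its list. For the age-4 EEG composite the plan adds: "Models will be examined with and without preregistered baseline covariates as above".

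Neither phase says which fit tests a registered hypothesis. The Multiple comparisons sections deal with families of outcomes, not with two fits of the same outcome.

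**The concern.** An analysis should respect the strata used in randomisation. Stratifying by site removes between-site variation from the treatment contrast, and a model without site terms puts that variation back into the residual. The reported standard error is then larger than the real sampling error, and the test rejects too rarely under the null.

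The second issue is the choice of fit. Two fits of one outcome will sometimes fall on opposite sides of the 5% line. With no deciding fit named in advance, the conclusion is unclear when they disagree, and the stated error rate holds only if readers can be sure the choice did not depend on the results.

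**Working it through.** **Inputs from the SAP.** Phase 1, Statistical power: "After accounting for likely 20% attrition in the age-4 lab visit", "the sample size of 800 at age 4, divided 40%/60% between high and low payment groups", so 320 against 480. Site sizes and 40/60 allocation are as quoted above. The share of variance explained by site, or by all of X, is not given. I assume 2-10% for site and 10-30% for all covariates including site.

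**The plan's own figure.** With SD = 1 and no covariates, SE = sqrt(1/320 + 1/480) = 0.0722. The two-sided detectable effect at 80% power is (1.960 + 0.842) × 0.0722 = 0.202, and the one-sided effect is (1.645 + 0.842) × 0.0722 = 0.179. These match the Phase 2 figures of .20 and .18. The Phase 1 figure of .219 for the same inputs does not reproduce, but that is a separate matter and nothing below depends on it.

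**Step 1: effect of omitting site on the reported SE.** With 40/60 in every site, the true variance is close to proportional to 1 − R²(site), while the no-X model reports a variance proportional to 1. The overstatement is 1/sqrt(1 − R²(site)):

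- R²(site) = 0.02: 1.010
- R²(site) = 0.05: 1.026
- R²(site) = 0.10: 1.054

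**Step 2: simulation.** The setting was exact 40/60 assignment in the four site sizes, random loss to 800, robust SEs and 6,000 null runs per setting (Monte Carlo error about sqrt(0.05 × 0.95/6000) = 0.3 points). With R²(site) = 0.10:

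- True SD of the estimate: 0.068-0.070 without site and 0.068-0.069 with site dummies, so almost no difference.
- Mean reported SE: 0.0722 without site and 0.0685 with site (ratio 1.054, as in step 1).
- Two-sided type I error without X: 4.0-4.4%. At R²(site) of 0.05 and 0.20 it was 4.6% and 3.1%. With site dummies alone it was 4.8-5.2% across these settings.

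Across all settings, the no-X and fully adjusted fits disagreed on significance in 3.4-4.9% of null runs.

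**Step 3: error rate if either fit could count.** The no-X statistic has variance 1 − R²(site) and the adjusted statistic has variance 1. Their correlation is sqrt[(1 − R²(all))/(1 − R²(site))]. The bivariate normal probability that at least one is significant at 5% is:

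| R²(site) | R²(all) | one-tailed | two-tailed |
|---|---|---|---|
| 0.02 | 0.10 | 6.1% | 6.2% |
| 0.02 | 0.30 | 7.1% | 7.3% |
| 0.05 | 0.20 | 6.4% | 6.5% |
| 0.10 | 0.10 | 5.0% | 5.0% |
| 0.10 | 0.30 | 6.4% | 6.5% |

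The low end arises when site is all that the covariates explain: the adjusted fit then rejects whenever the no-X fit does.

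**Step 4: what naming the adjusted fit gains.** The two-sided detectable effect at 800 is 0.202 × sqrt(1 − R²(all)): 0.192 at R²(all) = 0.10, 0.181 at 0.20 and 0.169 at 0.30.

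**The case against.** The best defence is that the plan already implies the adjusted fit. X is added for precision. The power section says covariates will improve power. The opening statement of the SAP calls these variables its list of controls, and the July 2025 addenda to both phases say without qualification that preregistered outcomes will be controlled for child age and, for interviews and assessments, for assessor. The Phase 1 Attrition section also gives the comparison with and without X its own purpose, as a check for attrition bias. All of this stands, and it makes the omission one of explicit designation rather than of intent. It does not close the gap: the power figures are computed without covariates, and no sentence designates a fit.

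The phrase about demographic child and family characteristics could also be read as leaving site in the base model. The list that follows, with the site dummies first, points the other way.

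Three stronger readings are tempting, and the documents do not support them.

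- A reader might infer that omitting site biases the estimate or wastes real precision. With the same allocation in every site it does neither to any material degree. The larger precision loss in the no-X fit comes from omitting the other prognostic covariates.
- A reader might infer that the plan already runs above 5%. No text lets either fit count. Rates of 6.3-7.3% one-tailed or 6.5-7.6% two-tailed (all covariates 10-30%) also require site to explain nothing, which contradicts the premise that omitting it matters.
- A reader might infer that every outcome is tested twice. The age-4 EEG secondary analyses and the age 6 and 8 EEG analyses list covariates without repeating an unadjusted fit, although the general strategy is said to apply to EEG measures.

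**Conclusion.** The point holds as a modest defect in specification. The no-X fit ignores the randomisation strata. Its reported SE is too wide by about 1-5% for a site R² of 2-10%, and its test is conservative. If site explains almost nothing, the cost is almost nothing.

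Separately, for outcomes under the general strategy and for the age-4 EEG composite, no deciding fit is named. The 5.0-7.1% (one-tailed) and 5.0-7.3% (two-tailed) rates are conditional: they apply only if either fit were allowed to count, and only under the assumed R² ranges and 40/60 balance within each site of the analysed sample. They show what an explicit designation would rule out and do not describe the plan as written.

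**What to change.** In both phases of the SAP:

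1. Keep the three site dummies in every model, so that the fit without covariates means treatment plus site.
2. State that the covariate-adjusted model tests each registered hypothesis, and say explicitly whether the child-age and assessor controls added in July 2025 are part of it. Leaving them unmentioned would leave a further specification open.
3. Report the treatment-plus-site model as a robustness check.

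The first change is free: it only makes the analysis follow the randomisation. The whole edit is a few sentences per phase and needs no new data, and both fits are still reported.

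The designation does carry a cost at age 4. Phase 2 reports age-4 data already gathered (634 for child EEG to 882 for maternal reports of behaviour problems) and refers to ongoing and preliminary age-4 EEG analyses. For those outcomes the SAP should disclose that the deciding model was named after data collection. The designation is fully prospective only for outcomes not yet analysed.
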